Investigating the effects of a spinal mobilisation intervention in people with lower back pain.

NCT number: 04012970

Date: 27/06/2016

Study Protocol

Participants

40 participants were recruited for this study via posters, social media and word of mouth. If interest in the study was shown, an information sheet with inclusion and exclusion criteria was given to the participant. If inclusion and exclusion criteria were met, the participant was randomly sorted into a group by a random group generator and testing sessions for the intervention and control were arranged.

Procedure

Participants were involved in both a control and a spinal mobilisation intervention session. All participants were informed about details of the study and provided written consent to take part. All data collection took place in the same treatment room at the Edinburgh Napier Sighthill campus, on the same standard physiotherapy plinth. Both sessions were arranged as close to the same time of day as possible to avoid additional environmental influences. Ambient room temperature was controlled (between 20° and 23° Celsius) for all sessions. All participants completed the Oswestry Disability Index (ODI) questionnaire and an ODI scoring sheet prior to their first session to categorise their level of lower back pain. Anthropometric measures for height, mass, waist circumference and gender were also taken.

Outcome measures for muscle stiffness, tone and elasticity were taken immediately before and after both sessions. The pre intervention stiffness measure determined which side the therapy was applied to. This was based on the greatest mean value for stiffness following 3 recorded measures, therefore working on the stiffer side of the spine. The location for measurements was identified on both sides of the spine on erector spinae (longissimus). Measurements were taken from the central belly of this muscle by asking the participant to lift their head and feet at the same time contracting their back muscles. This spot was marked to ensure pre and post measures were taken at the same location. The distance and width from the base of the spine was measured to locate the same spot for their 2nd session.

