The intervention was conducted by a physiotherapist with extensive experience in spinal mobilisation therapy. The intervention involved mobilisations on the lumbar spine (L1 to L5) for 30 minutes on the determined side of the participant lying prone. The control session involved no physical touch. The participant lay either prone or supine on the same plinth and encouraged to relax for 30 minutes.

Outcome measures

Measurements for para-spinal muscle stiffness, tone and elasticity were taken using a myometer palpation device (MyotonPRO). This previously validated handheld device has been documented to give reliable results for muscle stiffness, tone and elasticity. The myometer uses a series of low force mechanical impulses registered as an oscillation in the form of an acceleration signal. The stiffness, tone and elasticity parameters are reported as a mean of these impulses along with the coefficient of variation (CV). Values were only accepted if the CV was <3%, complying with the manufacturer recommendations.

Statistical Analysis Plan

Participant data was stored on password protected excel files on University computers. All participant names were replaced with a pseudonym and therefore participant data was not identifiable. Summary data was then used for statistical analysis.

Analysis was carried out on each dependent variable (muscle stiffness, tone and elasticity) in separate 2-way repeated measure within participant ANOVAs. This was to determine any significant differences occurring due to the independent variables (condition and time). Covariates were also assessed in separate ANCOVAs to determine any significant factors contributing to their changes. All statistical analysis was out using SPSS 23 with the alpha level set at 0.05.

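### The SAP names neither the condition-by-time term nor an effect estimate; a baseline-adjusted paired difference would define one per outcome and usually, not always, narrow its interval

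*Combined protocol and SAP*

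**What the plan says.** Every participant has both sessions (Study Protocol, Procedure): "Participants were involved in both a control and a spinal mobilisation intervention session". The same section gives the measurement times: "Outcome measures for muscle stiffness, tone and elasticity were taken immediately before and after both sessions". Each participant therefore supplies four values per outcome: pre and post, in each of two sessions.

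The Statistical Analysis Plan specifies: "Analysis was carried out on each dependent variable (muscle stiffness, tone and elasticity) in separate 2-way repeated measure within participant ANOVAs". Its aim is given as: "This was to determine any significant differences occurring due to the independent variables (condition and time"). It does not mention the interaction, an effect estimate, a confidence interval or a primary outcome.

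It then adds: "Covariates were also assessed in separate ANCOVAs to determine any significant factors contributing to their changes". The covariates are not listed, and the pre-session reading is not named as an adjustment in the session comparison.

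Two other statements bear on the point. Under Participants: "the participant was randomly sorted into a group by a random group generator". Under Procedure: "The pre intervention stiffness measure determined which side the therapy was applied to".

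**The concern.** A two-by-two within-participant ANOVA yields three tests: condition, time, and condition by time. Only the third asks whether the change differed between the mobilisation and control sessions. The condition main effect averages in readings taken before treatment, and the time main effect pools the two sessions. An aim worded as any significant difference leaves all three reportable as the result.

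The third test is also not the most precise use of the data in most settings. It subtracts the whole pre-session difference from the post-session difference, although regression would usually give it a smaller weight. At stake are the width of the interval from 40 participants and clarity about which number per outcome is the efficacy estimate.

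**Working it through.** **Inputs from the documents.** n = 40 (Participants); alpha 0.05 (Statistical Analysis Plan); pre and post readings in both sessions (Procedure). The documents give no power calculation, SD, correlation or effect size, so the plan has no figure of its own to reproduce.

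**Assumptions.** Two-sided testing and 40 complete participants. X and Y are the paired pre-session and post-session differences (intervention minus control), normally distributed with correlation r. Y has SD 1, and X has mean 0 and SD s. For power, the true effect is 0.45 SD of Y. Here r is the correlation of the between-session differences, not the ordinary pre-post correlation.

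**Step 1: what the ANOVA tests.** On one simulated data set with n = 40, the condition-by-time F(1,39) was 0.9212. The squared paired t statistic for the difference in raw changes was also 0.9212. The condition main effect, F = 4.937, equalled the squared t for the average of pre and post, which is not a comparison of changes.

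**Step 2: the two variances** (each to be divided by n).
- Raw change, Y − X: 1 + s² − 2rs, which is 2(1 − r) when s = 1.
- Adjusted (intercept of Y on uncentred X): (1 − r²) × (n − 2)/(n − 3) = (1 − r²) × 38/37.

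Before the factor 38/37, raw minus adjusted is (1 + s² − 2rs) − (1 − r²) = (s − r)². The slope is b = r/s, so this equals s²(1 − b)². The gain therefore disappears when the slope is near 1, whatever the value of r. The worst case, b = 1, is a variance ratio of 38/37 = 1.027.

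**Step 3: equal variances (s = 1, so b = r).** Raw power is from the noncentral t with 39 df; adjusted power is simulated, with 38 df.

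| r | Raw | Adjusted | Variance ratio | CI width ratio | Power, raw | Power, adjusted |
|---|---|---|---|---|---|---|
| 0.3 | 1.40 | 0.91 × 38/37 = 0.935 | 0.668 | 0.818 | 65% | 82% |
| 0.5 | 1.00 | 0.75 × 38/37 = 0.770 | 0.770 | 0.878 | 79% | 89% |
| 0.7 | 0.60 | 0.51 × 38/37 = 0.524 | 0.873 | 0.935 | 95% | 97% |
| 0.9 | 0.20 | 0.19 × 38/37 = 0.195 | 0.976 | 0.989 | >99% | >99% |

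At r = 0.5, 40 × 0.770 = 30.8, so about 31 participants analysed with adjustment match the precision of 40 analysed by raw change.

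**Step 4: unequal variances.**
- s = 0.8, r = 0.5 (b = 0.625): 0.770/0.84 = 0.917; power 86% to 89%.
- s = 0.8, r = 0.7 (b = 0.875): 0.524/0.52 = 1.007; power 97% for both.
- s = 0.8, r = 0.8 (b = 1): 0.370/0.36 = 1.027; the adjusted interval was the wider one in about 80% of simulated trials.
- s = 1.25, r = 0.5 (b = 0.4): 0.770/1.3125 = 0.587; power 68% to 88%.

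**Step 5: error rate.** With the mean of X equal to 0 and no effect, both tests rejected in about 5% of simulated trials. That condition can fail if the side is chosen from the readings. One assumed rule was simulated for stiffness: the control session uses the side picked from the pre-intervention reading. Over 27 assumed variance settings with no true effect, the interaction rejected in 6–17% of trials and the adjusted intercept in 5–8%.

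**The case against.** The case for leaving the plan alone has real weight.

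- **The interaction is a standard, legitimate analysis.** This stands. A reader might infer that the planned ANOVA is wrong. The documents do not support that: the ANOVA contains the right comparison, although the SAP does not name it.
- **The size of the gain is unknown and may be small.** This stands. The measurement spot is marked within a session but relocated by measured distance for the second. Relocation error is then shared by pre and post readings, which pushes r upwards. Very low correlations, where the gain looks most striking, are hard to defend.
- **A narrower interval is not guaranteed.** This stands. It is tempting to say that the gain fails only at very high r. Step 4 shows that it can fail at r = 0.7, because the slope is what matters. The asymmetry still favours adjustment: the variance loss is at most about 3%, against a possible saving of a quarter or more.
- **The SAP already has ANCOVAs.** This stands only in part. Baseline adjustment is unspecified rather than excluded. As described, though, those models look for factors behind the changes and do not adjust the session comparison for the pre-session difference.
- **Adjustment does not give the trial one efficacy result.** This stands. Three outcomes leave three estimates; at 0.05 each, the family-wise error is 1 − 0.95³ = 14% if they are independent.
- **Adjustment does not repair side selection.** This stands. A reader might also infer that the problem is confined to stiffness. The documents give no basis for that: tone and elasticity are read at the same site with the same device, and the side analysed in the control session is not stated.
- **The analysis may already have been run.** The SAP is written in the past tense. If so, the adjusted estimate can only be a labelled addition.

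**Conclusion.** The point holds as an optional improvement in efficiency and pre-specification. The firm part is that the SAP does not say which ANOVA term, or which estimate, answers the efficacy question for each outcome.

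The efficiency part depends on quantities the documents do not give. Under equal variances the saving in variance runs from about 33% at r = 0.3 to 2% at r = 0.9. It is nil or slightly negative when the slope is near 1. The interval is usually, not always, narrower.

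Reading the intercept as the treatment effect requires an expected pre-session difference of zero. That is reasonable if the random groups are session orders, which the protocol does not state, and if the analysed side is not selected from the pre-intervention reading. If it is so selected, neither test can be called unbiased for any of the three outcomes on the strength of this change.

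**What to change.** For each outcome, state in the SAP that the efficacy estimate is the intercept, with 95% CI, from a regression of the paired post-session difference (intervention minus control) on the paired pre-session difference. The pre-session difference should be left uncentred, so that the intercept is the session difference at equal pre-session readings. Report the condition-by-time interaction as supportive and the two main effects as descriptive. State whether the random groups are session orders.

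If the analysis has already been run, report the adjusted estimate beside the interaction and label it as added later.

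The cost is one degree of freedom (38 instead of 39) and one or two sentences, with no new data. Multiplicity over the three outcomes and the side analysed in the control session need separate statements.

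### If any reading is missing, the planned repeated-measures ANOVA drops that participant from the outcome; a pre-specified mixed model in the same software would keep the remaining data

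*Combined protocol and SAP*

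**What the plan says.** The Study Protocol (Participants, Procedure) describes a two-session design: "Participants were involved in both a control and a spinal mobilisation intervention session". On recruitment it says: "40 participants were recruited for this study via posters, social media and word of mouth". On allocation: "the participant was randomly sorted into a group by a random group generator". What the groups are, and the allocation ratio, are not stated; order of sessions is the natural reading.

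Each session yields two readings per outcome: "Outcome measures for muscle stiffness, tone and elasticity were taken immediately before and after both sessions". With two conditions and two times, each participant contributes four readings per outcome. A separate return visit is needed: "The distance and width from the base of the spine was measured to locate the same spot for their 2nd session".

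Under Outcome measures there is an acceptance rule: "Values were only accepted if the CV was <3%, complying with the manufacturer recommendations". Whether a failing reading is repeated or left empty is not said.

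The Statistical Analysis Plan then states: "Analysis was carried out on each dependent variable (muscle stiffness, tone and elasticity) in separate 2-way repeated measure within participant ANOVAs". Condition and time are the factors, the software is SPSS 23 and alpha is 0.05. The plan gives no number analysed, no dropout and no missing-data rule, and does not name the SPSS procedure.

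**The concern.** A classical two-way within-participant ANOVA uses only participants with all four cells filled. One empty cell removes the whole participant for that outcome, including a complete other session. The design has two possible routes to an empty cell: failure to return for the second session, and a reading that never meets the CV limit.

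Three things are at stake if cells are empty. Precision is lost from a sample of 40. The three outcomes may rest on different participants without the reader being able to tell. And the condition × time effect, which compares the change after mobilisation with the change after control, may be biased if those who drop out are selected by how they responded.

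**Working it through.** The plan contains no power, dropout or sample-size figure to reproduce. From the documents: 40 recruited, four readings per outcome, alpha 0.05 (taken as two-sided). Everything else below is an assumption.

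**Participants lost.** If each reading is missing independently with probability p, the share excluded is 1 − (1 − p)^4:

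- p = 1%, 2%, 3%, 5%: 3.9%, 7.8%, 11.5%, 18.5%.
- At p = 5%, 40 × 0.8145 = 32.6 participants remain; at p = 10%, 40 × 0.6561 = 26.2.

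Independence is a simplification: a missed session empties two cells at once, so for the same cell rate fewer people are affected.

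**Precision.** Take the change (post minus pre) in each session, with variance 1 and correlation ρ between a participant's two changes. Let m of 40 lack the second session, shared equally between orders, and n = 40 − m.

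- ANOVA variance of the effect: 2(1 − ρ)/n.
- Variance using all data: 2 / [n/(1 − ρ) + m/2].
- Ratio: 1 + (1 − ρ)m/(2n).

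| m (share) | n | Ratio, ρ = 0 | Ratio, ρ = 0.8 |
|---|---|---|---|
| 2 (5%) | 38 | 1 + 2/76 = 1.026 | 1.005 |
| 4 (10%) | 36 | 1 + 4/72 = 1.056 | 1.011 |
| 6 (15%) | 34 | 1 + 6/68 = 1.088 | 1.018 |
| 8 (20%) | 32 | 1 + 8/64 = 1.125 | 1.025 |

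On the standard-error scale the last row is 6.1% and 1.2%.

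**Bias.** Simulation of 600 trials per scenario: N = 40, balanced order, reading SD 1, variance components 0.70 (participant), 0.13 (participant × condition), 0.03 (participant × time) and 0.14 (residual), true effect −0.20, no period effect, about 20% non-return. The comparator is a REML mixed model with those three random effects. Simulation error in each bias is about 0.13/√600 = 0.005.

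| Non-return | ANOVA bias (coverage) | Mixed-model bias (coverage) |
|---|---|---|
| None | −0.003 (0.93) | −0.003 (0.93) |
| At random | −0.005 (0.97) | −0.005 (0.96) |
| Depends on session-one response, equally after either condition | +0.003 (0.94) | −0.005 (0.95) |
| Depends on session-one response, after mobilisation only | −0.085 (0.89) | −0.001 (0.94) |
| Depends on the unseen session-two response | −0.092 (0.88) | −0.107 (0.87) |

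In the fourth row the ANOVA bias is 0.085/0.20 = 43% of the assumed effect. A mixed model with only a random intercept left a bias of +0.020 there. With random non-return, power was 0.31 for the ANOVA and 0.35 for the mixed model. In a complete data set both gave −0.1959 with standard error 0.1085.

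A more extreme version, in which the 2, 4 or 6 worst-responding mobilisation-first participants do not return, gave ANOVA bias of about 0.09 to 0.10, 0.15 and 0.19 SD of a within-session change, with type I error of 7%, 11% and 13%. Maximum likelihood with an unstructured covariance estimated from the data had bias under 0.003 SD in the same scenario.

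**The case against.** The strongest reply is that nothing is shown to be missing. The protocol is written in the past tense, says participants had both sessions and says readings were taken before and after each. In that state the ANOVA is a valid standard analysis, and a mixed model would give the same estimate. This stands. A reader might infer that data were in fact discarded; the documents do not support that.

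The CV route is also uncertain. With a handheld device, a failing reading may simply be repeated, and three measures are mentioned for choosing the side. This stands as well: the documents do not say which happens.

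A reader might further infer that any link between response and return biases the ANOVA. It does not: with balanced order, equal dependence after either condition nearly cancels. The extreme scenario is one-sided by construction.

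Nor is the mixed model never worse or free of cost. When missingness depends on unseen session-two values, both analyses are biased to a similar degree. The precision gain is largest at zero correlation between changes and shrinks as that correlation rises.

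Finally, an unstructured covariance over four cells means ten parameters estimated from at most 40 people. Estimating it did not bring back bias in the simulation. However, the simulations assumed no period effect, and Satterthwaite degrees of freedom together with period terms were not themselves simulated.

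What survives is that the plan has no rule for an empty cell, and that its stated method handles one by discarding the participant.

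**Conclusion.** The point holds conditionally. If all 40 participants supplied all four accepted readings for every outcome, the choice of analysis makes no practical difference. If some did not, the planned ANOVA discards usable data. The variance cost is modest: about 3% to 13% at 5% to 20% non-return with uncorrelated changes, and 2.5% at 20% with correlation 0.8.

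The larger risk is bias when non-return depends on session-one response differently by condition or order. This is conceivable because one session is hands-on and the other involves no contact. A suitably specified mixed model removed that bias in simulation, provided missingness depended only on observed data. All missing rates, correlations and variance components are assumptions; the documents supply only the 40, the four readings and alpha.

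**What to change.** Replace the ANOVA with one linear mixed model per outcome in SPSS 23 MIXED:

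- REML with Satterthwaite degrees of freedom and an unstructured covariance over the four condition-by-time cells.
- Fixed effects: condition, time and condition × time, plus session period (first or second) and period × time, so that unequal loss between orders does not bring in a period effect.
- Every participant with at least one accepted reading is included. The plan states whether a reading failing the CV limit is repeated or treated as missing.
- Condition × time is reported as the treatment effect, with the number of readings by cell, outcome and order.
- The plan states that validity assumes missingness depends only on observed data, and adds a sensitivity analysis (for example, completers only) if any reading is missing. Completers only shows how far the result rests on partial participants; it does not test dependence on unseen values.

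The cost is a few lines of SAP text and a different procedure in software already named. The covariance structure and degrees of freedom must be fixed in advance, with a fallback if the unstructured model fails to converge; a random intercept alone is not an adequate fallback. With complete data and balanced order the estimated condition × time effect is unchanged, although the period terms may slightly alter its standard error and degrees of freedom.
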